## **7 Data review and database management**

### **7.1 Site monitoring**

Before study initiation, at a site initiation visit or at an investigator’s meeting, a Novartis representative will review the protocol and CRFs with the investigators and their staff. During the study, the field monitor will visit the site regularly to check the completeness of patient records, the accuracy of entries on the CRFs, the adherence to the protocol and to Good Clinical Practice, the progress of enrollment, and to ensure that investigational treatment is being stored, dispensed, and accounted for according to specifications. Key study personnel must be available to assist the field monitor during these visits.

The investigator must maintain source documents for each patient in the study, consisting of case and visit notes (hospital or clinic medical records) containing demographic and medical

information, laboratory data, electrocardiograms, and the results of any other tests or assessments. All information on CRFs must be traceable to these source documents in the patient's file. The investigator must also keep the original informed consent form signed by the patient (a signed copy is given to the patient).

The investigator must give the monitor access to all relevant source documents to confirm their consistency with the CRF entries. Novartis monitoring standards require full verification for the presence of informed consent, adherence to the inclusion/exclusion criteria, documentation of SAEs, and of data that will be used for all primary variables. Additional checks of the consistency of the source data with the CRFs are performed according to the study-specific monitoring plan. No information in source documents about the identity of the patients will be disclosed.

## **7.2 Data collection**

Designated investigator staff must enter the information required by the protocol onto the Novartis CRFs that are printed on 3 part, non-carbon-required paper. Field monitors will review the CRFs for completeness and accuracy and instruct site personnel to make any required corrections or additions. *CRO working on behalf of Novartis* by field monitors or by the investigational site, with one copy being retained at the investigational site. Once the CRFs are received by *CRO working on behalf of Novartis*, their receipt is recorded, the original copy is placed in Central Files, and the non-carbon-required copy is forwarded to the responsible Data Management staff for processing.

## **7.3 Database management and quality control**

Data from the CRFs are entered into the study database by CRO using double data entry. Verification is performed manually by a separate member of the Data Management staff by comparing the Case Report Form to the data entered into the database.

Data from the CRFs are entered into the study database by Data Management staff using double data entry and by referring to the scanned image of the CRF

Data from the CRFs are entered into the study database by Contract Research Organization (CRO) staff following their own internal standard operating procedures that have been reviewed and approved by Novartis.

Subsequently, the entered data are systematically checked by Data Management staff, using error messages printed from validation programs and database listings. Other errors or omissions are entered on Data Query Forms, which are returned to the investigational site for resolution. The signed original and resolved Data Query Forms are kept with the CRFs at the investigator site, and a copy is sent to Novartis so the resolutions can be entered into the database. Quality control audits of all key safety and efficacy data in the database are made prior to locking the database.

Concomitant medications entered into the database will be coded using the WHO Drug Reference List, which employs the Anatomical Therapeutic Chemical classification system. Concomitant procedures, non-drug therapies and adverse events will be coded using the Medical dictionary for regulatory activities (MedDRA) terminology.

Laboratory samples will be processed by institute and the results will be sent electronically to Investigator.

ECG readings will be processed by investigators and results will be recorded .

#### **7.4 Data Monitoring Committee**

Not required.

#### **7.5 Adjudication Committee**

Not required.

### **8 Data analysis**

#### **8.1 Analysis sets**

Investigators will enter the information required by the protocol into the Novartis Case Report Forms (CRFs). Non-obvious errors or omissions will be entered on Data Query Forms, which will be returned to the investigational site for resolution.

The data from all centers will be pooled and summarized with respect to demographic and baseline characteristics and efficacy and safety observations. [REDACTED]

[REDACTED] Data will be presented for the complete intent-to-treat population (all subjects having taken at least one dose of study medication) as well as the per-protocol population (all subjects who completed the study without major protocol deviations). Safety data will be evaluated for the safety population (all subjects having taken at least one dose and who have at least one post-baseline assessment).

Data summaries will be presented.

This trial is an exploratory study, and it is not powered for a statistical analysis. The statistical analyses of the measurements will be performed when possible, and these analysis will be done by the investigators and an independent Contract Research Organization.

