## SAE Serious adverse event Glossary of terms

Assessment	A procedure used to generate data required by the study
Cohort	A group of newly enrolled patients treated at a specific dose and regimen (i.e. treatment group) at the same time
Control drug	Any drug (an active drug or an inactive drug, such as a placebo) which is used as a comparator to the drug being tested in the trial
Dose level	The dose of drug given to the patient (total daily or weekly etc.)
Enrollment	Point/time of patient entry into the study at which informed consent must be obtained (i.e. prior to starting any of the procedures described in the protocol)
Epoch	A portion of the study which serves a specific purpose. Typical Epochs are: screening/recruitment, wash-out, treatment, and follow-up
Investigational drug	The drug whose properties are being tested in the study; this definition is consistent with US CFR 21 Section 312.3 and is synonymous with "investigational new drug" or "investigational medicinal product."
Investigational treatment	All investigational drug(s) whose properties are being tested in the study as well as their associated treatment controls. This includes any placebos, any active controls, as well as approved drugs used outside of their indication/approved dosage or tested in a fixed combination. Investigational treatment generally does not include protocol-specified concomitant background therapies when these are standard treatments in that indication
Medication number	A unique identifier on the label of each investigational/study drug package in studies that dispense medication using an IRT system
Protocol	A written account of all the procedures to be followed in a trial, which describes all the administrative, documentation, analytical and clinical processes used in the trial.
Part	A single component of a study which contains different objectives or populations within that single study. Common parts within a study are: a single dose part and a multiple dose part, or a part in patients with established disease and in those with newly-diagnosed disease.
Period	A subdivision of a cross-over study
Premature subject/patient withdrawal	Point/time when the patient exits from the study prior to the planned completion of all study treatment administration and/or assessments; at this time all study treatment administration is discontinued and no further assessments are planned, unless the patient will be followed for progression and/or survival

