### 3 Investigational plan

#### 3.1 Study design

The study will be conducted as an exploratory open-label pilot trial. There will be only one treatment arm. The improvement will be evaluated in comparison to the findings recorded at the baseline.

Figure 3-1 Study design

Approximately 10 subjects aged 18 to 60 years, who sign an informed consent and meet all inclusion and exclusion criteria in the screening period will enter into the study. The first dose of canakinumab will be administered as 300 mg IV.

At the end of the first month, an analysis will be conducted to assess the complete, partial, and non-responders to canakinumab treatment by physician.

Partial responders will be able to take the 2nd canakinumab dose as 300 mg IV infusion at the first month then will continue the canakinumab treatment with 150 mg IV infusions at monthly intervals for 4 times. The complete responders will continue the canakinumab treatment with 150 mg IV infusions at monthly intervals for 5 times. Non-responder or deteriorating patients will be dropped from the study at the first month evaluations.

At month 6, the patients will be able to switch to SC injections or continue as IV infusions of 150 mg canakinumab for additional 6 monthly administrations. Non-responder or deteriorating patients will be dropped from the study at the first month evaluations.

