### **3.4 Purpose and timing of interim analyses/design adaptations**

At the end of 1st month primary end point will be assessed by the physician. Complete / Partial / Non responders will be determined.

At 3rd and 6th months, there will be additional analyses to evaluate steroid tapering, prevention of disease exacerbation, and general disease activity by physician.

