#### **5.5.10 Withdrawal of consent**

Subjects also should be withdrawn at any time if the investigator concludes that it would be in the patient's best interest for any reason. Protocol deviations should not lead to patient withdrawal unless they indicate a significant risk to the patient's safety.

Subjects may voluntarily withdraw from the study for any reason at any time. They may be considered withdrawn if they state an intention to withdraw, or fail to return for visits, or become lost to follow up for any other reason.

If premature withdrawal occurs for any reason, the investigator must determine the primary reason for a patient's premature withdrawal from the study and record this information on the Study Completion CRF. For subjects who are lost to follow-up (i.e., those subjects whose status is unclear because they fail to appear for study visits without stating an intention to withdraw), the investigator should

show "due diligence" by documenting in the source documents steps taken to contact the patient, e.g., dates of telephone calls, registered letters, etc.

Every patient has the right to discontinue study participation at any time, and every patient may be discontinued from the study for any reason beneficial to his/her wellbeing. All data generated up to the time of discontinuation from the study will be analysed and the reason(s) for discontinuation will be recorded.

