## 5.7 Patient demographics/other baseline characteristics

Patient demographic and baseline characteristic data to be collected on all patients include: date of birth, age, sex, ethnicity, patient referral source, relevant medical history/current medical condition present before signing informed consent. Where possible, diagnoses will be recorded, not symptoms.

Subjects should be seen for all post-baseline visits on the designated day with the allowance of a  $\pm 7$  day window for all visits. Subjects who discontinue study drug before completing the study, and those who prematurely withdraw from the study for any reason, should be scheduled for a visit 8 weeks ( $\pm 1$  week) after their last infusion /injection, at which time all of the assessments listed for the final visit will be performed.

Subjects who discontinue study drug also should return for a last assessment. If they refuse to return for this or are unable to do so, every effort should be made to contact them or a knowledgeable informant by telephone to determine the reason for discontinuation. At a minimum, they will be contacted for safety evaluations during the 30 days following the last dose of study drug, including final contact at the 30-day point. Documentation of attempts to contact the patient should be recorded in the patient record.

Information that will be collected on subjects who are screened but not enrolled includes patient demographics (age, gender, and ethnicity) and primary reason for not continuing.

If a patient discontinues before entering Visit 1, only the demographic information and Screening Log entry with the primary reason for discontinuation should be completed on the CRF. It is not necessary to complete all the required evaluations at the time of discontinuation unless medically indicated.

At screening visit information on age, sex, will be collected. Relevant medical history/current medical conditions, family medical history, will be recorded on the respective CRF page. The following should be recorded on the respective CRF page.

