## **8.4 Analysis of the primary variable(s)**

### **8.4.1 Variable(s)**

Percentage of complete responders.

Symptoms measured by VAS.

Percentage of patients achieved appropriate steroid tapering.

Changes of general disease activity measured by BDCAF.

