### **8.4.2 Statistical model, hypothesis, and method of analysis**

To claim the efficacy of canakinumab on the resolution of attacks, at least 50% response will be aimed in at least 50% of the patients.

All parameters will be compared with baseline values. Complete / Partial / Non responders definitions can be seen in efficacy assessment section.

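### The per-protocol set admits only study completers, yet Day 30 non-responders are removed at month 1, so its Day 30 non-response is 0% by construction; the readable text names no set for the 50% criterion

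*Combined protocol and SAP*

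**What the plan says.** Section 8.1 (Analysis sets) presents data for the intent-to-treat population, meaning everyone who received at least one dose, "as well as the per-protocol population (all subjects who completed the study without major protocol deviations"). Neither is named as primary in the readable text, and some text just before that sentence is redacted.

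Section 3.1, repeated in 5.5.5, states: "Non-responder or deteriorating patients will be dropped from the study at the first month evaluations". Section 3.4 places the outcome at the same moment: "At the end of 1st month primary end point will be assessed by the physician", with patients sorted there into complete, partial and non-responders. Section 2.1 sets the primary endpoint at Day 30.

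Treatment is planned for one year and the visit schedule runs to Day 360. The glossary describes premature withdrawal as: "Point/time when the patient exits from the study prior to the planned completion of all study treatment administration and/or assessments".

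The first variable listed in 8.4.1 is "Percentage of complete responders", with no denominator. Section 8.4.2 sets the condition for claiming efficacy on attack resolution: "at least 50% response will be aimed in at least 50% of the patients". It does not name an analysis set.

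**The concern.** A per-protocol set should be selected on adherence to the protocol, not on the outcome being measured. Here the requirement to complete the study, combined with removal of non-responders at month 1, makes membership depend on the Day 30 response itself. The set has its failures taken out before the percentage is calculated.

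Two things are at stake. First, the per-protocol result for Day 30 cannot show non-response, so it says nothing about how often the drug fails. Second, 8.4.2 holds the only stated rule for claiming efficacy on attack resolution, and two reported sets can answer that rule differently in the same trial. The trial is open-label and single-arm, the physician judges response, and there is no adjudication committee, so the denominator is one of the few safeguards left.

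**Working it through.** **Plan's own figure.** Section 8.7 gives 10 patients with no effect size, power or formula, so there is no calculation to reproduce.

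**Step 1: set logic.**
- Per-protocol requires completing the study (8.1).
- A non-responder at the month-1 evaluation leaves the study then (3.1, 5.5.5).
- Leaving before the planned end of treatment or assessments is premature withdrawal (glossary), and the planned end is Day 360. Such a patient is not a completer.
- Hence the number of Day 30 non-responders in the per-protocol set is 0, and so is the rate.

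This assumes only that the removal rule is followed.

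**Step 2: effect on complete response.** Let C, P and R be the numbers of complete, partial and non-responders. Assume for now that everyone is classified and that nobody leaves later or has a major deviation.
- ITT: C/(C + P + R)
- Per-protocol: C/(C + P)

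The second exceeds the first exactly when C ≥ 1 and R ≥ 1. Example: C = 3, P = 3, R = 4 gives 3/10 = 30% in ITT and 3/6 = 50% in per-protocol. One trial misses a 50% target in one set and meets it in the other.

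Later dropout can reverse the direction. With C = 4, P = 4, R = 2 and three complete responders leaving later, ITT gives 4/10 = 40% and per-protocol gives 1/5 = 20%.

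**Step 3: how often the two sets disagree.** The documents give no expected response rates, so those below are assumptions. The criterion is read here as at least 50% complete responders, with n = 10, all patients classified and no later dropout.
- ITT meets it when C ≥ 5. With a 30% complete-response rate this is P(X ≥ 5), X ~ Binomial(10, 0.30), which is 0.1503.
- Per-protocol meets it when C ≥ P and C + P > 0. The probability is the sum, over all such counts, of 10!/(C! P! R!) × pC^C × pP^P × pR^R, where pC, pP and pR are the three assumed rates.
- C ≥ 5 of 10 implies C ≥ P, so meeting it in ITT implies meeting it in per-protocol. The chance of missing in ITT but meeting in per-protocol is therefore the difference.

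| Assumed complete / partial | ITT met | Per-protocol met | Missed in ITT, met in per-protocol |
|---|---|---|---|
| 30% / 30% | 15.0% | 58.0% | 43.0% |
| 20% / 40% | 3.3% | 26.1% | 22.8% |
| 30% / 60% | 15.0% | 19.4% | 4.4% |

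The gap is large when 40% of patients do not respond (first two rows) and small when 10% do not (last row).

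**Step 4: is complete-or-partial response then 100%?** Only if every completer is classed as complete or partial. The definitions do not guarantee this.
- Vascular (2.1 and 5.9.1): a patient with 60% improvement on both global VAS assessments, a 30% fall in CRP and a stable aneurysm is neither a complete nor a partial responder, because VAS and CRP must both fall in the same band. The same patient shows none of the listed features of non-response.
- Neurologic (2.1 and 5.9.1): complete and partial response both need CSF findings, but the visit schedule marks CSF puncture as optional.

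Such patients are not clearly caught by the removal rule and could complete the study.

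**The case against.** **ITT is there and is the natural choice.** It is defined, listed first and keeps the non-responders, while per-protocol is added as a companion. Section 8.4.2 speaks of the patients without restriction, and the redacted text in 8.1 may assign a set. This largely stands. A reader might infer that the sponsor means to rest its claim on the per-protocol set, and nothing in the documents says so. What remains is that the readable text leaves the choice open.

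**The data are not lost.** Section 5.5.10 says "All data generated up to the time of discontinuation from the study will be analysed", and under 5.7 early leavers, "and those who prematurely withdraw from the study for any reason, should be scheduled for a visit 8 weeks" after the last dose, have the final-visit assessments. This is correct for ITT. It does not make a patient removed at month 1 a completer, so it does not repair the per-protocol set.

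**A 100% per-protocol response rate does not follow.** A reader might infer from 0% non-response that complete-or-partial response must be 100% and that the criterion is met whenever the set contains anyone. Step 4 shows why the documents do not support that. Nor do they support an inference that the complete-response percentage is always pushed upward.

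**The magnitude is assumed.** The response rates are not the plan's, and 8.4.2 can be read in other ways, for instance as a 50% improvement within each patient. This stands, and the table is an illustration only. The set logic in Step 1 does not depend on it.

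**Later results properly concern responders.** Relapse and preservation of remission presuppose a response, and continuing only responders is the openly stated design. This stands. Labelling of later results is a reporting matter and does not carry the point.

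**The study is exploratory and unpowered.** This limits the harm, but 8.4.2 still sets a condition for an efficacy claim.

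**Conclusion.** The point holds in a limited form and should be fixed. As written, the per-protocol set excludes every Day 30 non-responder, so its Day 30 non-response is 0% regardless of drug effect. Confidence in this is high. It rests on the removal rule being followed and on completion meaning the planned one-year course.

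With no later dropout, the per-protocol complete-response percentage exceeds ITT whenever there is at least one complete responder and one non-responder. With later dropout it can move either way. In the illustration, the share of trials that miss a 50% complete-response target in ITT but meet it in per-protocol runs from 4.4% to 43.0%, under assumed rates and one reading of the criterion.

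That the criterion's analysis set is unnamed carries moderate confidence, given the redaction and the natural reading as ITT. The harm is confined to the per-protocol result and the choice of set for the claim.

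**What to change.** 1. **Section 8.1.** For Day 30 endpoints, define per-protocol as all ITT patients with no major protocol deviation up to the Day 30 assessment, regardless of response or later completion. If the present set is kept for 12-month results, call it *completers*.
2. **Section 8.4.2.** Name ITT (all dosed patients) as the set for the 50% criterion. Count dosed patients with no Day 30 assessment, or with no assignable response class, in the denominator as not responding. State which response definition the 50% response refers to, since naming the set alone leaves the criterion undetermined.
3. **Optional.** Label Day 90, 180 and 360 results as describing patients who continued after month 1, and show how many were removed.

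The clinical removal rule is not changed. The cost is wording and minor programming, with no new data or visits. The downside for the sponsor is less favourable per-protocol figures.

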### **5.5.4 Instructions for prescribing and taking study treatment**

All patients will receive study medication every four weeks. Patients will receive IV infusions of canakinumab in open label study treatment period. Please refer to for study schema description.

All study treatments assigned to the patient during the study will be recorded.

Each reconstituted vial provides 150 mg of canakinumab per 1 mL.

From a microbiological point of view, once the canakinumab solution for infusion has been compounded in the infusion bag or the solution for injection has been prepared, it should be used immediately. If not used immediately, it should be administered within 24 hours (end of infusion included). If the infusion solution/solution for injection is not used within 60 minutes of preparation, it should be kept at 2-8 °C. The bags and the solution for injection should be allowed to come to room temperature for 5-10 minutes but not more than 15 minutes before administration.

Detailed instructions on the preparation and administration of the study drug will be described in the Pharmacist Manual and provided to the site.

Patients should remain at the study site for observation for 1 hour following study drug administration.

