#### **5.5.13 Study completion and post-study treatment**

Information on the date the subject last took drug, the subject's completion or discontinuation of the study and the reason for discontinuation of the study will be recorded on the Study Completion CRF page.

Visit	Screening ***	1***	2	3	4	5	6	7	8	9	10	11	12	13	14	15
Day	-7 to 0	0	7	14	30	60	90	120	150	180	210	240	270	300	330	360
Blood biochemistry		X		X	X			X	X	X	X	X				
Inflammatory markers	X	X	X	X	X	X	X	X	X	X	X	X	X	X	X	X
Urine Test	X	X	X	X	X	X	X	X	X	X	X	X	X	X	X	X
PK markers		X	X		X	X	X			X		X				X
PD samples		X	X		X	X	X			X		X				X
MR-Doppler Imaging (PET-CT when necessary)		X	X	X	X	X	X			X		X				X
(*)CSF Puncture	X			X	X		X									
Neurological evaluation		X	X	X	X	X	X	X	X	X	X	X	X	X	X	X
BDCA (BD Current Activity)	X	X	X	X	X	X	X	X	X	X	X	X	X	X	X	X
Adverse Events	X	X	X	X	X	X	X	X	X	X	X	X	X	X	X	X
VAS for symptoms	X	X	X	X	X	X	X	X	X	X	X	X	X	X	X	X
Efficacy Assessment					X		X			X						X
Attack Assessment	X	X	X	X	X	X	X	X	X	X	X	X	X	X	X	X
Steroid usage assessment	X	X	X	X	X	X	X	X	X	X	X	X	X	X	X	X
Physician&Patient Global Assessment		X	X	X	X	X	X	X	X	X	X	X	X	X	X	X
Drug Administration		X			X	X	X	X	X	X	X	X	X	X	X	X

\*Optional

\*\* PPD test could be used within 6 months before patient study entry

**\*\*\* If needed, in Patient's emergency situation, Screening and Visit 1 assessment could be combining by the physician decisions. There is no need to be repeated same test for each visit (screening and visit 1)**

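### The safety population in Section 8.1 requires a post-baseline assessment as well as a dose, so it can be smaller than the all-dosed set and depend on what happens after dosing (minor).

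*Combined protocol and SAP*

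**What the plan says.** The document is a combined protocol and SAP. Section 8.1 defines two sets that matter here.

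- The "intent-to-treat population (all subjects having taken at least one dose of study medication"). A dose is the only requirement.
- The "safety population (all subjects having taken at least one dose and who have at least one post-baseline assessment"). A second requirement is added, and safety data are to be evaluated in this set.

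Section 8.2 uses the safety population for the demographic and baseline tables. Section 8.5.2 summarises adverse events by number and percentage of subjects and names no other set. Section 8.3 (exposure) names no set.

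The glossary describes an assessment only as a procedure that generates study data. Section 5.5.8 identifies the baseline visit as Day 0. Nothing visible says which type of procedure or contact, or which time, meets the added requirement. Section 8.1 is partly redacted, but both definitions are legible in full.

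**The concern.** Safety is part of the primary objective (Section 2), and adverse-event frequency is its main summary (Section 8.5.2). A safety denominator is normally fixed by exposure alone, so that nothing after dosing can remove a patient from it. Here a patient can be dosed and still fall outside the set because of what followed. The set used for harm is then stricter than the ITT set.

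Two analysts could also build different sets from the same data, because several kinds of contact may or may not qualify:

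- The on-site observation in Section 5.5.4: "Patients should remain at the study site for observation for 1 hour following study drug administration". It takes place on Day 0 at the first dose, so it is unclear whether it is post-baseline.
- The telephone follow-up in Section 5.7 for patients who stop: "they will be contacted for safety evaluations during the 30 days following the last dose of study drug".
- An adverse event or SAE reported between visits, which Section 6.1 allows for.

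If none of these counts, a patient who dies or is lost before the first visit after dosing leaves both the numerator and the denominator. That would sit poorly with Section 5.5.10, under which all data up to discontinuation are analysed, and with the inclusion of all SAEs in Section 8.5.2. Neither section states a denominator, so this is a tension and not a flat contradiction.

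**Working it through.** **Inputs.** Planned number of patients: 10 (Sections 3.1 and 8.7). First scheduled visit after dosing: Day 7 (schedule in Section 5.5.13), with a window of ±7 days (Section 5.7), so as late as Day 14. Rate of dosed patients with no later assessment: not given. The plan states no figure that could be reproduced on this point.

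**Step 1: the relation between the sets.** Safety set = dosed and assessed; ITT set = dosed. The safety set is a subset of ITT, and strictly smaller whenever a dosed patient has no qualifying assessment.

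**Step 2: strict, visit-based reading.** Section 5.7 attaches the term to visits: "Subjects should be seen for all post-baseline visits on the designated day". Suppose 10 patients are dosed, one is excluded and that patient is a known case. Then x/10 becomes (x−1)/9, a fall of x/10 − (x−1)/9 = (10−x)/90. Intervals are exact (Clopper-Pearson) 95%.

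| Events among 10 | All dosed | Tabulated | Fall |
|---|---|---|---|
| 1 | 1/10 = 10% (0.3–44.5%) | 0/9 = 0% (0–33.6%) | 10.0 points |
| 3 | 3/10 = 30% (6.7–65.2%) | 2/9 = 22.2% (2.8–60.0%) | 7.8 points |
| 5 | 5/10 = 50% (18.7–81.3%) | 4/9 = 44.4% (13.7–78.8%) | 5.6 points |

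If the excluded patient is known to have had no event, the rate rises instead: 3/10 = 30% becomes 3/9 = 33.3%.

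**Step 3: inclusive reading.** The schedule has a row headed "Adverse Events", so a recorded post-dose event can itself be an assessment. Known cases then stay in, and only a patient with no post-dose data drops out. With x cases among the 9 followed, the table shows x/9. The all-dosed rate lies between x/10 (the missing patient had no event) and (x+1)/10 (the patient had one). The gaps are x/9 − x/10 = x/90 and (x+1)/10 − x/9 = (9−x)/90. Neither is negative for x from 0 to 9, so x/9 always lies inside the range.

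| x | Tabulated x/9 | All-dosed range | Above lower end | Below upper end |
|---|---|---|---|---|
| 0 | 0% | 0–10% | 0 | 10.0 points |
| 2 | 22.2% | 20–30% | 2.2 points | 7.8 points |
| 4 | 44.4% | 40–50% | 4.4 points | 5.6 points |

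**Step 4: how often it might arise.** With an assumed per-patient probability q of having no qualifying assessment, the chance that at least one of 10 is affected is 1 − (1−q)^10: 9.6% for q = 1%, 18.3% for 2%, 40.1% for 5% and 65.1% for 10%. These values of q are assumptions for illustration only; nothing in the documents supports one over another.

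**The case against.** The case for leaving the text alone has several parts.

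- **The term is not without meaning.** The glossary and the Day 0 baseline together point to any study procedure that generates data after baseline. This stands. A reader might infer that the condition is wholly undefined, but the documents do not support that. What remains open is which type, timing and mode of contact qualifies.
- **The strict reading is the weaker one.** Section 8.1 speaks of an assessment, not a visit; adverse events are a scheduled assessment item; Section 6.1 accepts events found between visits; and Section 5.5.6 provides for repeat CSF or imaging in the first week if there is no response or worsening. This stands too, so the fall from 10% to 0% should not be read as the expected effect.
- **The condition has a purpose.** It keeps patients with no post-dose data from diluting the rates. A reader might infer that it brings no benefit at all; that goes too far, since an all-dosed denominator in effect counts such patients as event-free.
- **Few patients can be affected.** Besides the one-hour observation there are visits on Days 7, 14 and 30, tracing through family or physician (Section 5.5.11), telephone safety contacts, and a visit 8 weeks after the last dose, "at which time all of the assessments listed for the final visit will be performed". This makes the trigger improbable but does not exclude it.
- **Other outputs cover part of the gap.** Section 8.1 also says "Data will be presented for the complete intent-to-treat population", and its pooling sentence mentions safety as well as efficacy observations. Yet it then assigns safety evaluation to the narrower set, so the all-dosed safety tables are not assured.
- **No decision depends on it.** The study is exploratory and single-arm, and Section 8.5.2 plans no safety test, threshold or interval. This limits the weight of the point but does not justify the wording.

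**Conclusion.** The concern holds as a minor point. By its own wording the safety population can be smaller than the all-dosed set, and membership depends on what happens after dosing. The effect is confined to the denominators and rates of the safety tables and the baseline tables.

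For 10 dosed patients and one exclusion, the largest distortion is 10 percentage points. On the strict reading this requires that the excluded patient be the only case. On the more natural inclusive reading no known case is lost, the tabulated rate stays within the all-dosed range, and the direction of error is unknown. The likelihood is not given and is probably low in view of the follow-up arrangements.

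A reader might infer that the plan would conceal an early death or serious event. The documents do not support that: Section 6.2.2 requires every SAE from consent to 30 days after the last administration to be reported individually to the sponsor within 24 hours, whether or not a visit took place. Nor is any figure in the plan shown to be wrong.

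**What to change.** In Section 8.1, define the safety population as all patients who received any canakinumab, and drop the post-baseline requirement. State that this set is used for Sections 8.2, 8.3 and 8.5.2. Count every adverse event and SAE after the first dose, whether or not a visit took place. Add a footnote to the adverse-event table giving the number of dosed patients with no post-dose follow-up.

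The cost is a short rewording of Section 8.1 and one table footnote, with no new data and no change to patient management. The downside is that a dosed patient with no follow-up enters the denominator as if event-free, so the reported rate is the lower end of the range in Step 3 and slightly diluted. The footnote makes this visible and lets a reader work out the upper end.
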